**Table 5–6: Second Supplementary Estimand: ICEs and Strategies to address them**

ICEs**	Reason for ICE	Strategy	Data handling method
Temporary Treatment interruption*	AEs (treatment related/unrelated)	Treatment policy	Utilise the collected data after ICE.
	COVID-19 and administrative reasons	Hypothetical If participant complied with treatment	Model outcomes during the ICE under the hypothetical scenario.
Permanent discontinuation of randomized treatment	AEs (treatment related/unrelated) or Lack of efficacy		
	For participants who remained untreated/on background therapy.	Treatment policy	Utilise the collected data after ICE.
	For participants who initiate alternative VMS treatment	Composite Treatment failure (i.e., no change from baseline)	Model outcomes after the ICE under the treatment failure.
Intake of prohibited concomitant medication having impact on efficacy	Other treatment-unrelated reasons, including COVID-19	Hypothetical If participant did not discontinue the randomized treatment.	Model outcomes after the ICE under the hypothetical scenario.
	All reasons	Composite Treatment failure (i.e., no change from baseline)	Model outcomes under the treatment failure during the period of confounding.

ICE=Intercurrent event, AE=Adverse event, VMS = Vasomotor symptoms

\*Definition of temporary treatment interruption:

Week 1 = Treatment taken on <5/7 days during week 1.

Week 4 = Treatment taken <80% during weeks 1-4 OR treatment taken on <5/7 days during either week 3 or 4.

Week 8 = Treatment taken <80% during weeks 1-8 OR treatment taken on <5/7 days during either week 7 or 8.

Week 12= Treatment taken <80% during weeks 1-12 OR treatment taken on <5/7 days during either week 11 or 12.

\*\*ICEs will be reviewed prior to the study unblinding.

**Table 5–7: Second supplementary estimand data handling and missing data imputation strategy.**

Pattern ID	ICE and the associated reason	ICE strategy and data handling	Reference group for modeling the distribution of missing or unobservable data
NA	Intake of prohibited medications	Composite strategy Treatment failure (i.e., no improvement from baseline.)	N/A
	Any reason	Discard the collected data after the intake of prohibited medication(s) for a certain time	

		frame based in the medication class (See Section 6.5.3 for details) and assign the value of zero change from baseline.	
1	Temporary treatment interruption  Due to COVID-19 /administrative or any other treatment unrelated reasons	Hypothetical strategy  If participant complied with treatment.  Data collected for a specific assessment during/after a temporary treatment interruption will be discarded for that assessment Week only.	Participants, from the same arm, who comply** with treatment regimen and have observed data at the time point that requires imputation. (same as the first supplementary analysis)
2	Temporary treatment interruption  Due to AE	Treatment policy strategy  Utilize all the collected data in the analysis.	Participants, from the same arm, who have available data before and during the treatment interruption.  MI will be used to model change from a time point before treatment interruption to a time point with treatment interruption (Copy Increment from Reference imputation strategy). (same as the first supplementary analysis)
3	Permanent treatment discontinuation  (Due to AE/lack of efficacy)	Treatment policy strategy  If participant remained untreated/on background therapy after permanent discontinuation of the randomized treatment, use the treatment policy strategy and utilize the collected data.	Missing values that occur after the ICE will be imputed using a similar MI model as used in the main analysis of the primary endpoint, i.e., the MI regression model will include auxiliary variables indicating (yes/no) whether the participant continued on randomized treatment at each visit (Guizzaro et al., 2021). (same as the first supplementary analysis)

		Composite strategy  Otherwise, if participant initiated an alternative treatment, use the composite strategy assuming treatment failure (i.e. no change from baseline). Discard data after the ICE and impute with participant's baseline value.	N/A
4	Permanent treatment discontinuation.  Due to COVID-19 /administrative or any other treatment unrelated reasons	Hypothetical strategy  If participant did not discontinue the randomized treatment due to the specified reason.  Any data collected after permanent treatment discontinuation will be discarded	All other participants from the same arm (i.e., participants without a similar ICE at the time point that requires imputation). (same as the first supplementary analysis) .

\*\* Complying with treatment regimen is defined as having no ICEs (i.e. no early discontinuation of randomized treatment, no treatment interruption in the respective week (definition in [Table 1–2](#)) and no intake of prohibited medication).

## 5.4 Secondary Endpoints Analysis

The secondary efficacy endpoints in this study are:

- Mean change in PROMIS SD SF 8b total score from baseline over time
- Mean change in MENQOL total score from baseline over time

The calculation of the scores for PROMIS SD SF 8b and for the MENQOL total score will be done according to the respective questionnaire guidelines.

### 5.4.1 Definition of Endpoints

#### 5.4.1.1 Patient-reported Outcomes Measurement Information System Sleep Disturbance Short Form 8b (PROMIS SD SF 8b) related endpoint

- Mean change in PROMIS SD SF 8b total score from baseline over time

Participants responses to the 8 single items of the instrument are scored on a 1-5 numeric rating scale and aggregated to derive total raw scores ranging from 8 to 40. These total raw scores are then converted into T-scores using a look-up table for comparison with population norms. See further details in Section [6.2.2](#).

#### 5.4.1.2 Menopause Specific Quality of Life Scale (MENQOL) related endpoint

- Mean change in MENQOL total score from baseline over time

Participants responses to the 29 items will be scored individually on a scale indicating whether the participant experienced the symptom (yes/no). If they select yes, they rate how bothered they were by the symptom using a 6-point verbal descriptor scale. The items assess four domains of symptoms and functioning: vasomotor symptoms, psychosocial functioning,

physical functioning, and sexual functioning. Domain scores are calculated as mean of single item converted scores. The MENQOL total score is the mean of the domain mean scores. See details on Section [6.2.3](#).

#### 5.4.2 Main Analytical Approach

PROMIS SF 8b total raw scores, converted T-scores and MENQOL total scores will be summarized descriptively by treatment group and week using the number of non-missing observations, arithmetic mean and standard deviation, median, minimum and maximum. The absolute values at various weeks and the corresponding change from baseline per week will be summarized accordingly. The change from baseline over time in the PROMIS SF 8b T-scores and MENQOL total scores will be shown using line plots together with 95% CIs by treatment group.

Graphical summaries with the absolute change from baseline on the x-axis and proportion of participants achieving this change on the y-axis, by treatment group, for week 12 and 52 will be presented for the MENQOL total score and for the PROMIS SD SF 8b T-score.

In addition, PROMIS SD SF 8b raw score for each item will be summarized by a frequency table with the number of observation and percentage by treatment group and by week. Bar charts will also be created by treatment group over time.

For possible imputation of missing values, see section [5.1.1.1](#).

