#### **9.4.3 Secondary Endpoints**

The secondary efficacy endpoints in this study are:

- Mean change in PROMIS SD SF 8b total score from baseline over time
- Mean change in MENQOL total score from baseline over time

The calculation of the scores for PROMIS SD SF 8b, and for the MENQOL total score will be done according to the respective questionnaire guidelines. Details will be provided in the SAP.

The change from baseline for the secondary endpoints will be analyzed descriptively by treatment group using the number of non-missing observations, arithmetic mean and standard deviation, median, minimum and maximum using the FAS. In addition to the change from baseline over time, the values at various weeks will also be summarized accordingly.

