## 2. Statistical Hypotheses

$H_0: \mu_P \leq \mu_V$  versus  $H_1: \mu_P > \mu_V$  where  $\mu_P$  and  $\mu_V$  stand for the mean change in frequency of moderate to severe HF from baseline in the placebo (P) and verum (V) group to Week 12.

The type I error rate will be controlled at a one-sided  $\alpha=0.025$  level.

All other endpoints will be summarized descriptively and therefore no multiplicity adjustment is needed.

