- In the descriptive tables, data collected after premature discontinuation of treatment will not be shown for the respective treatment week. Assessments occurring up to 2 days after discontinuation (inclusive) will still be considered under treatment and shown for the respective week. Out of the assessment collected post treatment discontinuation (+ 2 days), the one closest to the planned time point of follow-up (i.e. discontinuation date + 28 days) will be shown as follow-up assessment. In case two assessments are equally close to that date, the first one will be selected.

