### 5.5 Exploratory Endpoints Analysis

The following exploratory endpoints will be analyzed by descriptive statistical methods as described in Section [5.1](#) by treatment group. The analysis will be based on the FAS. The ICEs will be handled according to the treatment policy. No missing data imputation is planned for the exploratory endpoints.

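### PROMIS and MENQOL have no pre-specified between-arm comparison or intercurrent-event strategy, and their treatment-week tables show on-treatment data only

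*SAP*

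**What the plan says.** **Objective and method.** SAP Table 1–1 makes it a secondary objective to evaluate efficacy on sleep quality and menopause-related quality of life. Protocol 9.4.3 plans, on the FAS: "The change from baseline for the secondary endpoints will be analyzed descriptively by treatment group using the number of non-missing observations", with mean, SD, median and range. SAP 5.4.2 repeats this: the scores "will be summarized descriptively by treatment group and week using the number of non-missing observations" and the same statistics. It adds line plots with 95% CIs for each arm, plots of the proportion reaching each level of change at Weeks 12 and 52, and PROMIS item tables and bar charts. SAP 2 gives the inferential position: "All other endpoints will be summarized descriptively and therefore no multiplicity adjustment is needed". The only estimands defined are for the primary endpoint, and SAP 5.1.1 rules out imputing missing secondary assessments unless otherwise specified.

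**Data after stopping drug.** For PROMIS and MENQOL, SAP 5.1.2 (text after Table 5–2) states: "In the descriptive tables, data collected after premature discontinuation of treatment will not be shown for the respective treatment week". There is a grace period: "Assessments occurring up to 2 days after discontinuation (inclusive) will still be considered under treatment and shown for the respective week". Of the later assessments, "the one closest to the planned time point of follow-up (i.e. discontinuation date + 28 days) will be shown as follow-up assessment". Protocol 7.1 asks women who stop drug to stay in the study until Visit T9 and, if they agree, to continue the scheduled visits and procedures.

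**Exploratory endpoints.** SAP 5.5 says of these: "The ICEs will be handled according to the treatment policy". They include the HFDD endpoints in 5.5.1 and the MENQOL domain and item scores in 5.5.2.

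**The concern.** Protocol 4.2 justifies the placebo arm by a placebo response of up to 60%, so that a drug effect can only be described against placebo. For sleep and quality of life the plan stops short of that comparison. It shows two sets of arm summaries and leaves the reader to compare them.

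The treatment-week rows also depend on who is still taking drug. Remaining on drug is a post-randomisation outcome that can differ between arms for reasons such as tolerability or lack of effect. By Week 52 a comparison of those rows is no longer a comparison of the groups as randomised. The data needed for that comparison are being collected from women who stop drug and stay in the study, but no treatment-week result uses them.

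**Working it through.** **Inputs.** There are 300 participants per arm. In the elinzanetant arm, drop-out is 10% in months 1–3, 10% in months 4–6 and 30% over the year (SAP 3, protocol 9.2). Neither document gives an SD, expected difference or power for PROMIS or MENQOL, so precision is given below in SD units.

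**1. The plan's own figures.** 300 × 0.9 = 270, 300 × 0.8 = 240 and 300 × 0.7 = 210, as stated. The primary-endpoint power in SAP Table 3–1 (t-test, 270 per arm, SD 4.29, one-sided 0.025) also reproduces: 77.1%, 98.2% and 99.97% for differences of 1.0, 1.5 and 2.0.

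**2. Where post-discontinuation data go.**
- Primary HFDD endpoint: kept out of the descriptive tables but used in the model (SAP 5.1.2). The strategy is treatment policy.
- PROMIS and MENQOL totals: kept out of the treatment-week rows, with no model. No strategy is stated.
- MENQOL domain and item scores and exploratory HFDD endpoints: kept out of the treatment-week summaries, and analysed only descriptively. The stated strategy is treatment policy, which those tables cannot deliver.

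The SAP 5.1.2 rule refers to tables. Whether it also governs the line plots is not stated.

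**3. How many participants.** At the planned rates, 300 − 270 = 30 per arm are lost by Week 12, and 300 − 210 = 90 in the elinzanetant arm are not treated for 1 year. Only those who stop drug but stay in the study have later values to recover.

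**4. Effect on the contrast (illustration).** Let d be the share discontinued, equal in both arms. Let r be the share of the on-treatment effect that discontinuers keep, with all of them observed and no other difference between those who stop and those who stay. The treatment-policy contrast is then [(1 − d) + d·r] times the on-treatment contrast, and the overstatement is the inverse.
- d = 0.10: r = 0 gives 1/0.900 = 1.11; r = 0.75 gives 1/0.975 = 1.03.
- d = 0.30: r = 0 gives 1/0.700 = 1.43; r = 0.75 gives 1/0.925 = 1.08.

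**5. Cost of not adjusting for baseline.** With equal variances at baseline and follow-up, and correlation ρ between them, the variance ratio of ANCOVA to raw change is (1 − ρ²)/[2(1 − ρ)] = (1 + ρ)/2. This is 0.65 at ρ = 0.3, 0.75 at 0.5 and 0.85 at 0.7, so variance falls by 35%, 25% and 15%. The correlations are assumed.

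**6. Precision available.** The unadjusted 95% half-width for a difference is about 1.96 × √(2/n). This is 0.17 SD with 270 per arm (Week 12) and 0.19 SD with 210 per arm (Week 52, if 30% applies to both arms).

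**The case against.** The strongest defence is that descriptive-only analysis is a declared choice, made consistently in protocol 9.1 and 9.4.3 and SAP 2 and 5.4.2. Sample size was set by safety exposure, and one efficacy endpoint was kept as confirmatory. That stands: the missing comparison is a design weakness, not a contradiction. But having no formal test is no reason to omit an estimate, and SAP 5.1 already allows 95% CIs where appropriate.

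Several stronger readings are tempting and are not supported:
- **That the trial yields no estimate at all.** The n, mean and SD by arm give a crude observed-case difference and interval. What is missing is a pre-specified, adjusted one with a stated estimand.
- **That everything after discontinuation is removed, leaving completers instead of the FAS.** There is a 2-day grace period and one follow-up assessment. Each row holds every FAS participant with a value on treatment that week, including women who stop later. The restriction is on observations, not on the analysis set.
- **That the secondary endpoints contradict SAP 5.5.** Its treatment-policy sentence covers the exploratory endpoints only. The secondary endpoints have no stated strategy to contradict.

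**Conclusion.** The point holds in limited form. For PROMIS and MENQOL totals there is no pre-specified contrast, interval or intercurrent-event strategy, and the treatment-week table rows are on-treatment. The mismatch between SAP 5.5 and the table rules in 5.1.2 is a real inconsistency, confined to the exploratory endpoints.

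The overstatement of 1.03 to 1.11 times at 10% discontinuation and 1.08 to 1.43 times at 30% rests wholly on the assumptions in step 4. The 30% is planned for the elinzanetant arm only, and participants who leave the study cannot be recovered.

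A reader might also multiply 30% by an assumed gap of, say, 5 T-score points and call the resulting 1.5 points a bias in the drug effect. That is a shift in one arm's mean. It cancels in the difference if both arms lose the same share with the same gap, and the documents give neither the size nor the direction of such a gap.

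The primary analysis is unaffected. This is a worthwhile and inexpensive improvement.

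**What to change.** 1. Show PROMIS T-score and MENQOL total by scheduled week using all collected FAS data, including post-discontinuation values. Keep the on-treatment version as an extra, and say which rule the figures follow.
2. State a treatment-policy strategy for both endpoints. Fit an MMRM with the Table 5–3 terms (baseline, region, treatment, week, treatment by week, baseline by week), on observed data under MAR and without imputing missing assessments, which is consistent with SAP 5.1.1.
3. Use each instrument's own post-baseline weeks through Week 52. Table 5–3 cannot be reused unchanged: it stops at Week 12, and it includes Week 1, for which Table 5–2 schedules no MENQOL.
4. Report elinzanetant minus placebo with a nominal 95% CI at Weeks 12 and 52, labelled as not controlled for multiplicity and with no significance claim.
5. Reconcile SAP 5.5 with the table rules in 5.1.2 for the exploratory endpoints.

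The cost is some extra tables, a re-specified model and SAP wording. No new data, alpha or participants are needed. The nominal intervals must not be read as confirmatory, and the MAR assumption remains for women who leave the study.

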### 5.5 Exploratory Endpoints Analysis

The following exploratory endpoints will be analyzed by descriptive statistical methods as described in Section [5.1](#) by treatment group. The analysis will be based on the FAS. The ICEs will be handled according to the treatment policy. No missing data imputation is planned for the exploratory endpoints.

#### 5.5.1 HFDD related exploratory endpoints

- Mean change in frequency of moderate to severe HF from baseline over time (assessed by HFDD)
- Mean change in severity of moderate to severe HF from baseline over time (assessed by HFDD)
- Mean change in frequency of mild, moderate, and severe HF from baseline over time (assessed by HFDD)
- Mean change in frequency of nighttime awakening from baseline over time (assessed by HFDD)
- Mean change in proportion of days with participant rating of ‘quite a bit’ or ‘very much’ sleep disturbances experienced due to HF from baseline over time (assessed by HFDD).

The mean change in frequency of mild, moderate, and severe HF from baseline over time will be calculated similar to the mean change in frequency of moderate to severe HF described in Section [5.1.2.1](#), but will also include mild HF in the calculation. Specifically, the baseline

value of the frequency of mild, moderate, and severe HF will be calculated by aggregating the available days during the 14 days prior to start of treatment to a mean daily frequency as (total number of mild, moderate, and severe HF during the 14 days prior to start of treatment) / (total number of available days with data). As per inclusion criteria 9 (see protocol), at least 11 days will be available for the derivation of the baseline value. Similarly, the frequency of mild, moderate, and severe HF for each week during the treatment period will be calculated using the available data during that particular week and aggregated to a mean daily frequency as (total number of mild, moderate, and severe HF during that week) / (total number of available days with data during that week). In case data is not available for more than 2 days within a week, the value for that week will be set to missing and no imputation of missing values will be performed. The mean change from baseline will then be calculated as the difference in the mean daily frequency of mild, moderate, and severe HF for a given week from the corresponding baseline value.

Calculation of mean change in severity of moderate to severe HF has been described in section 5.1.2.1. Summary statistics for the change from baseline in severity of moderate to severe HF and change from baseline in the frequency of mild, moderate, and severe HF will be summarized similar to change in frequency of moderate to severe HFs presented in Section 5.3.1. Relative change (%) from baseline will be additionally displayed only for the severity of moderate to severe HFs. The change from baseline, relative change from baseline in severity of moderate to severe HF over time and the change from baseline in the frequency of mild, moderate, and severe HFs over time will be shown using line plots for means together with 95% CIs by treatment group.

A graphical summary with relative change (%) (0 to 100) in the frequency and severity of moderate to severe HF from baseline on the x-axis and proportion of participants achieving this reduction on the y-axis, by treatment group, for week 12 and 52 will also be provided. Similarly, a graphical summary with absolute change in the frequency and severity of moderate to severe HF from baseline on the x-axis and proportion of participants achieving this change on the y-axis, by treatment group, for week 12 and 52 will also be produced.

The mean change in frequency of nighttime awakenings from baseline over time is based on the number of nighttime awakenings during the previous night that is being assessed every morning as part of the HFDD (morning diary). The baseline value of the nighttime awakenings will be calculated by averaging the nighttime awakenings from the available days during the 14 days prior to start of treatment to a mean daily frequency as (total number of nighttime awakenings during the 14 days prior to start of treatment) / (total number of available days with morning data). Similarly, the frequency of nighttime awakenings for each week during the treatment period will be calculated using the available data during that particular week and averaged to a mean daily frequency as (total number of nighttime awakenings during that week) / (total number of available days with morning data during that week). In case morning data is missing for more than 2 days within a week, the value for that week will be set to missing and no imputation of missing values will be performed. The mean change from baseline will then be calculated as the difference in the mean daily frequency of nighttime awakening for a given week from the corresponding baseline value.

Summary statistics in frequency of nighttime awakenings as well as the absolute change from baseline will be presented by weekly until Week 12 and at Weeks 23, 24, 35, 36, 49 and 50 thereafter by treatment group. The change from baseline over time in the frequency of nighttime awakenings will be shown using line plots for means together with 95% CIs by treatment group. A graphical summary with absolute change (0 to 100) in the frequency of

nighttime awakenings from baseline on the x-axis and proportion of participants achieving this reduction on the y-axis, by treatment group, for week 12 and 52 will also be provided.

The calculation using HFDD for Week 1 will be based on Days 2-8 on treatment, where Day 1 corresponds to start of treatment. Week 2 will be based on days 8-14, Week 3 will be based on days 15-21 and so on.

Sleep disturbances due to HF are assessed every morning as part of the HFDD (morning diary). Participants provide a rating of their sleep disturbances due to HF in the previous night as

- ‘not at all’
- ‘a little bit’
- ‘somewhat’
- ‘quite a bit’
- ‘very much’

To calculate the mean change in proportion of days with participants having reported ‘quite a bit’ or ‘very much’ sleep disturbance due to HF, the number of days with participants having reported ‘quite a bit’ or ‘very much’ sleep disturbance will be used. The baseline value of the proportion of days with participants having reported ‘quite a bit’ or ‘very much’ sleep disturbances due to HF will be calculated based on the available days during the 14 days prior to start of treatment as (number of days with sleep disturbance due to HF rated as ‘quite a bit’ or ‘very much’)/ (total number of available days with morning data). The on-treatment value for the sleep disturbances due to HF for each week will be calculated using the available data during that particular week as (number of days with sleep disturbance due to HF rated as ‘quite a bit’ or ‘very much’ during that week) / (total number of available days with morning data during that week). In case morning data is missing for more than 2 days within a week, the value for that week will be set to missing and no imputation of missing values will be performed. Mean change in proportion of days with participants having reported ‘quite a bit’ or ‘very much’ sleep disturbance due to HF from baseline will then be calculated as the difference in the mean sleep disturbance value for a given week from the corresponding baseline value.

Summary statistics for the proportion of days with participants having reported ‘quite a bit’ or ‘very much’ sleep disturbance due to HF as well as the absolute change from baseline will be presented by week and by treatment group. The change from baseline over time of the proportion of days with participants having reported ‘quite a bit’ or ‘very much’ sleep disturbance due to HF by treatment group will be shown using line plots for means together with 95% CIs by treatment group.

